5.1.1.4.4 Vital Signs

Vital signs will be summarized by treatment group for the Safety Population as follows:

Table 5-23 Vital Signs Summaries

Endpoint	Description	Timing	Methodology
PCS values ¹	Summary of number and percentage of participants by parameter and PCS criteria 
 Parameters and PCS criteria specified in Section 6.3.6.1 	Randomization to End of Study ¹	PCS descriptives
Descriptives ³	Summary by parameter and analysis visit 
 Parameters specified in Section 6.3.6.2 	Randomization to End of Study ²	CFB descriptives
Measures	Summary of number number and percentage of	Randomization to	Summary

Endpoint	Description	Timing	Methodology
meeting criteria ⁴	participants with post-treatment vital sign measurement meeting any of following criteria will by treatment group: 
 • Systolic Blood Pressure: < 90 mmHg, > 140 mmHg, > 160 mmHg • Diastolic Blood Pressure: < 50 mmHg, > 90 mmHg, > 100 mmHg • Pulse Rate: < 60 bpm, > 100 bpm • Temperature: > 38.0 °C, < 36.0 °C • Respiratory rate: < 12 breaths/min, > 20 breaths/min 	End of Study ²	

¹ Participants who report ≥ 1 postbaseline PCS value will have their vital sign visits with PCS values and all AEs listed.

² Analysis visits defined in Section 6.2.2.

³ Participant vital signs will be listed.

⁴ A listing of AEs for participants with postbaseline values meeting the criteria will be also provided.

5.1.1.4.5 Electrocardiograms

Electrocardiograms (ECGs) will be summarized by treatment group for the Safety Population as follows:

Table 5-24 ECG Summaries

Endpoint	Description	Timing	Methodology
PCS values ¹	Summary of number and percentage of participants by parameter and PCS criteria 
 • Parameters and PCS criteria specified in Section 6.3.7.2 • N1 (percentage denominator) = Participants with non-missing non-PCS baseline and ≥ 1 postbaseline parameter assessment 	Randomization to End of Study ²	PCS descriptives
Descriptives	Summary by parameter and analysis visit 
 • Parameters specified in Section 6.3.7.3 	Randomization to End of Study ²	CFB descriptives
Shift from baseline	Summary by parameter and category 
 • Normal; abnormal, not clinically significant; abnormal, clinically significant provided by investigator • Parameters specified in Section 6.3.7.3 	End of Study ²	Shift analysis
Clinically significant ECG abnormalities	A listing showing ECG parameters for participants with postbaseline clinically significant ECG abnormalities according to the investigator's overall interpretation	Randomization to End of Study ²	Listing
Descriptives of measures meeting criteria	Summary of number and percentage of participants with post-treatment QTcF >450 ms, >480 ms, and >500 ms will be tabulated by treatment group	Randomization to End of Study ²	Descriptives

¹ Participants who report ≥ 1 postbaseline PCS value will have their ECG visits with PCS values and all AEs listed.

² Analysis visits defined in Section 6.2.2.

5.1.1.4.6 Cardiovascular Risk

Patients will be categorized into 1 of 3 coronary heart disease (CHD) risk subgroups (low, moderate, or high risk) based on NCEP ATP III guideline. Subgroup analyses of TEAEs by cardiovascular (CV) risk category will be provided for the Safety Population.

Table 5-25 Cardiovascular Risk Summaries

Endpoint	Description	Timing	Methodology
TEAEs	
 Subgroup analyses by CV risk category for overall summary and by SOC and PT 	From randomization date to Visit 16 for participants with Visit 16, or within 30 days after last visit or last treatment, whichever is later, for participants without Visit 16	Categorical descriptives

5.1.1.4.7 Suicidality Analyses

Suicidality will be summarized by treatment group for the Safety Population as follows:

Table 5-26 Suicidality Summaries

Endpoint	Description	Timing	Methodology
C-SSRS ¹	Summary by number and percentage of participants with suicidal ideation and suicidal behavior for each study phase listed in the timing column	Lifetime History, 6 months prior to Screening in the lead-in study, Treatment phase, Safety Follow-up phase	Categorical descriptives

¹ Participants with all values, including participant number, treatment group, visit number, intensity of suicidal ideation, suicidal behavior type, and lethality of suicidal behavior will be listed.

5.1.1.5 Subgroup Analyses

Subgroups analyses will be done for disposition (Table 5-6), treatment exposure (Table 5-16), and TEAEs (Table 5-19) for sex, age group (<40 vs ≥40, and <65 vs ≥65), race (White vs. all other races), cardiovascular risk category, and renal function class.

5.1.1.6 Interim Analyses

The interim analysis will occur when at least 300 ubrogepant participants (with a minimum of 2 migraines treated with ubrogepant per month, on average) have been enrolled in the study for 6 months, and 200 ubrogepant participants (with a minimum of 2 migraines treated with ubrogepant per month, on average) have been enrolled in the study for 1 year.

The treatment assignments will be unblinded to the Allergan staff for the interim analyses. The interim analyses will include all analyses specified in this SAP except for efficacy analyses.

[REDACTED]

5.2 Changes in the Conduct of the Study or Planned Analyses

Prior to database lock, there were no changes in study conduct or planned analyses from what was described in the protocol and detailed in the SAP.

5.2.1 Changes in the Conduct of the Study

Not applicable.

6.2.2 Safety

The safety analysis visit windows for 3-month time interval are defined as follows:

Table 6-4 Safety Analysis Visit Definitions for 3-Month Time Interval

Analysis Phase	Analysis Visit (Derived)	Window
Treatment	Completed 3 months	Treatment Day \geq 90
	Completed 6 months	Treatment Day \geq 180
	Completed 9 months	Treatment Day \geq 270
	Completed 12 months	Completing treatment period per disposition CRF, or discontinued after day 360

Table 6-5 Safety Analysis Visit Definitions for 1-Month Time Interval

Analysis Phase	Analysis Visit (Derived)	Window
Treatment	Months 1	Treatment Day [1, 30]
	Months 2	Treatment Day [31, 60]
	Months 3	Treatment Day [61, 90]
	Months 4	Treatment Day [91, 120]
	Months 5	Treatment Day [121, 150]
	Months 6	Treatment Day [151, 180]
	Months 7	Treatment Day [181, 210]
	Months 8	Treatment Day [211, 240]
	Months 9	Treatment Day [241, 270]
	Months 10	Treatment Day [271, 300]
	Months 11	Treatment Day [301, 330]
	Months 12	Treatment Day [331, end of treatment period]

The analysis visit windows for safety endpoints are defined as follows:

Table 6-6 Safety Analysis Visit Definitions

Analysis Phase	Analysis Visit (Derived)	Scheduled Study Visit (eCRF)	Window
Pretreatment	Baseline	Baseline from Lead-in Study	Treatment Day \leq 1
	Week 4	(Visit 3) Week 4	Treatment Day [2, 42]
	Week 8	(Visit 4) Week 8	Treatment Day [43, 70]
	Week 12	(Visit 5) Week 12	Treatment Day [71, 98]
	Week 16	(Visit 6) Week 16	Treatment Day [99, 126]
	Week 20	(Visit 7) Week 20	Treatment Day [127, 154]
	Week 24	(Visit 8) Week 24	Treatment Day [155, 182]
	Week 28	(Visit 9) Week 28	Treatment Day [183, 210]
	Week 32	(Visit 10) Week 32	Treatment Day [211, 238]
	Week 36	(Visit 11) Week 36	Treatment Day [239, 266]
	Week 40	(Visit 12) Week 40	Treatment Day [267, 294]
	Week 44	(Visit 13) Week 44	Treatment Day [295, 322]
	Week 48	(Visit 14) Week 48	Treatment Day [323, 350]
	Week 52	(Visit 15) Week 52/Early Termination	Treatment Day [351, end of treatment period]

Analysis Phase	Analysis Visit (Derived)	Scheduled Study Visit (eCRF)	Window
	Safety Follow-up	(Visit 16) 4 Week Safety Follow-up	Treatment Day [end of treatment period+1, the last study visit]
	End of study	Final or termination visit	Latest non-missing assessment after randomization date

Safety follow-up visit will be presented in analysis tables for clinical laboratory values and vital signs.

End of Study is defined as the last available assessment during treatment and/or safety follow-up period. End of Study results will be presented in analysis tables for safety parameters, including but not limited to electrocardiograms, clinical laboratory values, and vital signs.

The following general conventions for repeated or unscheduled assessments will apply unless otherwise specified:

- The latest non-missing assessment within any analysis window will be flagged as the analysis value for any summaries by analysis visit
- All postbaseline assessments will be considered for PCS categorization
- All assessments will be included in respective listings

[REDACTED]

[REDACTED]

[REDACTED]	[REDACTED]	[REDACTED]	[REDACTED]	[REDACTED]	[REDACTED]	[REDACTED]
[REDACTED]	[REDACTED]	[REDACTED]	[REDACTED]	[REDACTED]	[REDACTED]	[REDACTED]
[REDACTED]	[REDACTED]	[REDACTED]	[REDACTED]	[REDACTED]	[REDACTED]	[REDACTED]
[REDACTED]	[REDACTED]	[REDACTED]	[REDACTED]	[REDACTED]	[REDACTED]	[REDACTED]
[REDACTED]	[REDACTED]	[REDACTED]	[REDACTED]	[REDACTED]	[REDACTED]	[REDACTED]
[REDACTED]	[REDACTED]	[REDACTED]	[REDACTED]	[REDACTED]	[REDACTED]	[REDACTED]
[REDACTED]	[REDACTED]	[REDACTED]	[REDACTED]	[REDACTED]	[REDACTED]	[REDACTED]
[REDACTED]	[REDACTED]	[REDACTED]	[REDACTED]	[REDACTED]	[REDACTED]	[REDACTED]
[REDACTED]	[REDACTED]	[REDACTED]	[REDACTED]	[REDACTED]	[REDACTED]	[REDACTED]
[REDACTED]	[REDACTED]	[REDACTED]	[REDACTED]	[REDACTED]	[REDACTED]	[REDACTED]

[REDACTED]

[REDACTED]

[REDACTED]	[REDACTED]	[REDACTED]	[REDACTED]	[REDACTED]	[REDACTED]	[REDACTED]
[REDACTED]	[REDACTED]	[REDACTED]	[REDACTED]	[REDACTED]	[REDACTED]	[REDACTED]
[REDACTED]	[REDACTED]	[REDACTED]	[REDACTED]	[REDACTED]	[REDACTED]	[REDACTED]
[REDACTED]	[REDACTED]	[REDACTED]	[REDACTED]	[REDACTED]	[REDACTED]	[REDACTED]
[REDACTED]	[REDACTED]	[REDACTED]	[REDACTED]	[REDACTED]	[REDACTED]	[REDACTED]
[REDACTED]	[REDACTED]	[REDACTED]	[REDACTED]	[REDACTED]	[REDACTED]	[REDACTED]
[REDACTED]	[REDACTED]	[REDACTED]	[REDACTED]	[REDACTED]	[REDACTED]	[REDACTED]
[REDACTED]	[REDACTED]	[REDACTED]	[REDACTED]	[REDACTED]	[REDACTED]	[REDACTED]
[REDACTED]	[REDACTED]	[REDACTED]	[REDACTED]	[REDACTED]	[REDACTED]	[REDACTED]
[REDACTED]	[REDACTED]	[REDACTED]	[REDACTED]	[REDACTED]	[REDACTED]	[REDACTED]

[REDACTED]

| [REDACTED]
| [REDACTED]
| [REDACTED]
| [REDACTED]

[REDACTED] [REDACTED]
[REDACTED]

| [REDACTED]
| [REDACTED]

[REDACTED] [REDACTED]
[REDACTED]

| [REDACTED]
| [REDACTED]

[REDACTED] [REDACTED]
[REDACTED]

| [REDACTED]
| [REDACTED]

[REDACTED] [REDACTED]

[REDACTED] [REDACTED]
[REDACTED]

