5.1.1.1.3 Statistical Methodology

The methodologies defined below apply as specified to individual endpoints defined in this SAP. All statistical tests will be 2-sided hypothesis tests performed at the 5% level of significance for main effects. All confidence intervals will be 2-sided 95% confidence intervals, unless stated otherwise.

Table 5-2 Statistical Methodology

Methodology	Description
M1 Categorical counts	
 • Number of participants in individual categories 
 ○ Participants with ≥ 1 qualifying event counted once per individual category
M2 Categorical descriptives	
 • Number and percentage of participants in individual categories 
 ○ Participants with ≥ 1 qualifying event counted once per individual category • N1 if proportion denominator \neq number of participants in the population (standard percentage denominator) 
 ○ N1 = participants with non-missing baseline value
M3 PCS descriptives	
 • Number and percentage of participants meeting potentially clinically significant (PCS) criteria 
 ○ Participants with ≥ 1 qualifying event counted once per PCS category • Percentage denominator = number of participants with all non-missing non-PCS baseline and ≥ 1 non-missing postbaseline assessment 
 ○ Unevaluable assessments considered missing
M4 Shift analysis	
 • Number and percentage of participants in individual baseline and postbaseline categories • Percentage denominator = number of participants in individual baseline categories • N1 = participants with non-missing values at both baseline and the specified postbaseline analysis visit
M5 Continuous descriptives	
 • N1, mean, standard deviation (SD), median, minimum, maximum • N1 = participants with non-missing value
M6 CFB descriptives	
 • Continuous descriptives for baseline, postbaseline, and change from baseline (CFB) values • N1 = participants with non-missing values at both baseline and the specified postbaseline analysis visit

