5.1.1.4.3 Clinical Laboratory Assessments

Clinical laboratory assessments will be summarized by treatment group for the Safety Population as follows:

Table 5-21 Clinical Laboratory Summaries

Endpoint	Description	Timing	Methodology
Number and percentage of participants with Potentially Clinically Significant (PCS) values ¹	Summary by laboratory category, parameter, and PCS criteria 
 Parameters and PCS criteria specified in Section 6.3.5.1 N1 (percentage denominator) = Participants with non-missing non-PCS baseline and ≥ 1 postbaseline parameter assessment 	Randomization to End of Study ³	PCS descriptives
Descriptives ²	Summary by laboratory category and parameter in SI units and in conventional units and analysis visit 
 Parameters specified in Section 6.3.5.3 	Randomization to End of Study ³	CFB descriptives
Shift from baseline	Summary by laboratory parameter and category 
 Low, normal, and high categories provided by central laboratory Parameters specified in Section 6.3.5.3 	End of Study ³	Shift analysis
Liver function findings ⁴	Summary of number and percentage by hepatic laboratory parameter and PCS categories. Definition of PCS categories see Table 6-10 in Section 6.3.4.2.	Randomization to End of Study ³	Categorical descriptives
Adjudication results of ALT or AST elevations ⁵	Summary of relationship of ALT or AST elevation to study medication for participants with adjudicated case (i.e., ALT $\geq 3 \times$ ULN and/or AST $\geq 3 \times$ ULN) by the following categories: 
 Probable Possible Unlikely Insufficient data Summary will be provided for the incidence by number of participants and by number of events	Randomization date to End of Study ³	Categorical descriptives

ALT = aspartate aminotransferase; AST = aspartate aminotransferase; TBL = total bilirubin; ALP = alkaline phosphatase; INR = international normalized ratio; ULN = upper limit of normal.

¹ Participants who report ≥ 1 postbaseline PCS value will have their laboratory visits with PCS values and all AEs listed.

² Clinical laboratory results and comments will be listed.

³ Analysis visits defined in Section 6.2.2.

Endpoint	Description	Timing	Methodology
----------	-------------	--------	-------------

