6.3.5 Clinical Laboratory Assessments

6.3.5.1 Potentially Clinically Significant Criteria

Laboratory assessments values meeting *any* of the following PCS low or PCS high criteria will be categorized as PCS:

Table 6-12 Clinical Laboratory PCS Criteria

Laboratory Group	Parameter	SI Unit	PCS Low Limit	PCS High Limit
Hematology	Basophils, absolute cell count	$10^9/L$	—	$> 2.0 \times ULN$
	Eosinophils absolute cell count	$10^9/L$	—	$> 2 \times ULN$
	Hematocrit	Ratio	$< 0.9 \times LLN$	$> 1.1 \times ULN$
	Hemoglobin	g/L	$< 0.9 \times LLN$	$> 1.1 \times ULN$
	Lymphocytes absolute cell count	$10^9/L$	$< 0.7 \times LLN$	$> 1.3 \times ULN$
	Monocytes, absolute cell count	$10^9/L$	$< 0.5 \times LLN$	$> 2.0 \times ULN$
	Neutrophils absolute cell count	$10^9/L$	$< 0.7 \times LLN$	$> 1.3 \times ULN$
	Platelet count (thrombocytes)	$10^9/L$	$< 0.5 \times LLN$	$> 1.5 \times ULN$
	Red blood cell count	$10^{12}/L$	$< 0.9 \times LLN$	$> 1.1 \times ULN$
	White blood cell count	$10^9/L$	$< 0.9 \times LLN$	$> 1.5 \times ULN$
Chemistry	Alanine aminotransferase	U/L	—	$> 3 \times ULN$
	Albumin	g/L	$< 0.8 \times LLN$	$> 1.2 \times ULN$

Laboratory Group	Parameter	SI Unit	PCS Low Limit	PCS High Limit
	Alkaline phosphatase	U/L	—	> 3 × ULN
	Aspartate aminotransferase	U/L	—	> 3 × ULN
	Bicarbonate	mmol/L	< 0.9 × LLN	> 1.1 × ULN
	Bilirubin, total	μmol/L	—	> 1.5 × ULN
	Blood urea nitrogen	mmol/L	—	> 1.5 × ULN
	Calcium	mmol/L	< 0.9 × LLN	> 1.1 × ULN
	Chloride	mmol/L	< 0.9 × LLN	> 1.1 × ULN
	Cholesterol, total	mmol/L	—	> 1.6 × ULN
	Creatinine	μmol/L	—	> 1.5 × ULN
	Creatine kinase	U/L	—	> 2.0 × ULN
	Glucose, nonfasting	mmol/L	< 0.8 × LLN	> 2 × ULN
	Lactate dehydrogenase (LDH)	U/L	—	> 3.0 × ULN
	Phosphorus	mmol/L	< 0.9 × LLN	> 1.1 × ULN
	Potassium	mmol/L	< 0.9 × LLN	> 1.1 × ULN
	Protein, total	g/L	< 0.9 × LLN	> 1.1 × ULN
	Sodium	mmol/L	< 0.9 × LLN	> 1.1 × ULN
	Triglycerides	mmol/L	—	> 2.0 × ULN
	Uric acid (urate)	μmol/L	—	> 1.2 × ULN
Urinalysis	Glucose	mmol/L	—	Positive
	pH	pH	< 0.9 × LLN	> 1.1 × ULN
	Protein	g/L	—	Positive
	Specific gravity	—	—	> 1.1 × ULN

LLN = lower limit of normal (value provided by the laboratory); PCS = potentially clinically significant; SI = *Le Système International d'Unités* (International System of Units); ULN = upper limit of normal (value provided by the laboratory).

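### The only readable laboratory low/normal/high shift runs to a last value that mixes treatment-period and follow-up samples; an End of Treatment shift would separate them.

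*SAP*

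**What the plan says.** **Timepoint.** Protocol 7.3.2.3 asks for laboratory shift tables from baseline to end of study, by treatment group. SAP Table 5-21 does this: the categories are "Low, normal, and high categories provided by central laboratory", and the timing column names End of Study alone.

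**Definition.** SAP 6.2.2 says "End of Study is defined as the last available assessment during treatment and/or safety follow-up period". The matching row of Table 6-6 reads "Latest non-missing assessment after randomization date".

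**Follow-up samples.** Laboratory values do exist at Visit 16: under Table 6-6 the SAP states "Safety follow-up visit will be presented in analysis tables for clinical laboratory values and vital signs". Protocol 8.8 expects participants who stop early to attend this visit as well, 4 weeks after Visit 15/ET.

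**Week 52/Early Termination row.** Its window is "Treatment Day [351, end of treatment period"].

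**Other laboratory output.** Table 5-21 also plans PCS counts, for which "All postbaseline assessments will be considered for PCS categorization"; counts by multiples of ULN for the liver tests (categories in Table 6-13); and by-visit summaries, which under method M6 of Table 5-2 are "Continuous descriptives for baseline, postbaseline, and change from baseline (CFB) values".

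**The concern.** Safety is the primary outcome (Protocol 3), and the usual-care arm is there to put safety findings in the ubrogepant arms into context (Protocol 1). The shift table is the plan's general patient-level count, by arm, of values outside the normal range. It rests on central-laboratory categories, so it depends less than AE reporting does on investigator judgement, which matters in a study that is open-label against usual care.

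The End of Study value does not come from the same phase for everyone. Where a Visit 16 laboratory value exists, it displaces the treatment-period value. Participants assigned to ubrogepant have by then left the treatment period by about 4 weeks, whereas the usual-care arm has no ubrogepant to stop. If ubrogepant caused a laboratory change that reverses, the contrast with usual care in this table would shrink.

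**Working it through.** **1. Which value enters the shift table**

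| Participant | End of Study value |
|---|---|
| Has a Visit 16 laboratory value | Visit 16 (about 4 weeks after the treatment period) |
| Has none | Last treatment-period value |

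This follows directly from SAP 6.2.2 and Table 6-6. It applies to completers and to participants who stop early.

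**2. Whether another row of Table 6-6 supplies the last treatment-period value**

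The Week 52/Early Termination window opens on Day 351. An early-termination sample on Day 120 falls in Days 99 to 126, which is the Week 16 row. No row holds the last treatment-period value for all participants.

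**3. What the PCS and liver counts leave uncounted**

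Shift parameters (Table 6-14): 22 chemistry + 13 hematology + 2 urinalysis = 37. Set against Table 6-12, where a value meeting any "of the following PCS low or PCS high criteria will be categorized as PCS":

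| PCS limits | Number | Parameters |
|---|---|---|
| None | 5 | HDL, LDL, MCV, MCH, MCHC |
| High only, non-hepatic | 10 | basophils, eosinophils, BUN, total cholesterol, creatinine, CK, LDH, triglycerides, uric acid, urine specific gravity |
| High only, hepatic | 4 | ALT, AST, total bilirubin, ALP |
| Low and high | 18 | the rest; 11 of them at 0.9 x LLN and 1.1 x ULN |

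Check: 5 + 10 + 4 + 18 = 37.

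For the four hepatic tests, Table 6-13 counts high values from 1 x ULN upward. It has no low category. (Table 5-21 points to Table 6-10 in Section 6.3.4.2 for these categories, but they are in Table 6-13, Section 6.3.5.2.)

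Examples of values that no readable table counts by arm if they are normal again at the last sample: creatinine between 1 and 1.5 x ULN, CK between 1 and 2 x ULN, platelets between 0.5 and 1 x LLN.

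**4. Size of the dilution**

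The plan gives no figure to reproduce. Let p be the share of participants with a Visit 16 laboratory value and r the share of the excess shifts that are normal by then. Assume that p is the same for participants with and without a shift, and that no new shifts arise after treatment. Then

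share of the treatment-period excess still shown = 1 - p x r.

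| p (assumed) | r = 0 | r = 0.5 | r = 1 |
|---|---|---|---|
| 0.5 | 1.00 | 0.75 | 0.50 |
| 0.9 | 1.00 | 0.55 | 0.10 |

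Neither p nor r is in the documents, so the result runs from no loss to near-complete loss. Shifts that resolve mid-study are a separate matter, which comes from using a single last value, and are not in this formula.

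**5. Whether a highest/lowest-value shift is a clean alternative**

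It is not. With a chance q per assessment of crossing one limit, independent across k assessments, the chance of at least one crossing is 1 - (1 - q)^k. Table 6-6 has 13 treatment-period visits (Weeks 4 to 52). The laboratory schedule is not readable, so k = 10 and k = 13 are illustrations.

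| q (assumed) | k = 10 | k = 13 | Gap with no drug effect |
|---|---|---|---|
| 0.025 | 22.4% | 28.0% | 5.7 points |
| 0.01 | 9.6% | 12.2% | 2.7 points |

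The gap falls to 0 if visits are perfectly correlated. Unequal dropout could therefore create an arm difference in such a table by itself.

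**The case against.** The case against acting is substantial. The SAP delivers what the protocol asks for. PCS tables already give a count at any time, by arm, using every postbaseline value, so the plan can be read as a division of labour: PCS for excursions, the shift table for final status. Treatment-period and follow-up values are kept apart in the by-visit descriptives, where Safety Follow-up has its own row, so a general excess that reverses by Visit 16 would show as a difference between rows. Abnormal laboratory findings can be reported as AEs (Protocol 9.1.1), and TEAEs are tabulated by 3-month onset interval (SAP Table 5-20). The effect size is assumed. Dosing is per attack, so a Visit 15/ET sample may itself be long after the last dose, which narrows any contrast with Visit 16.

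All of this stands as partial cover. It does not supply the missing count. M6 gives means, medians and extremes but no numbers of patients out of range. PCS counts start only beyond their limits and exclude participants who are already PCS at baseline. AE reporting depends on the investigator's view of the value (Protocol 6.2.3).

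A reader might go further and infer that reversible laboratory signals in 33 of the 37 parameters (37 minus the four liver tests) would go unseen. The documents do not support that. Of those 33, 28 have a PCS limit in at least one direction, and the descriptives, listings and AE tables still show values and events. The figure also treats the liver tests as fully covered, although Table 6-13 counts high values only.

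**Conclusion.** The point holds as a limitation of one planned display. It is worth correcting because the correction is cheap. The only readable low/normal/high laboratory count takes a follow-up value for anyone who has one and a treatment-period value for everyone else, and no visit row repairs this. A reversible excess in the ubrogepant arms is diluted in that table.

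The count that is missing is of out-of-range values that reach no PCS limit and are normal by the last sample. The gap is plainest for the 5 parameters with no PCS limit and for low values of the 10 non-hepatic parameters with a high limit only. For 11 parameters it is a band of 10% beyond each end of the normal range.

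The size of the dilution cannot be derived and may be small. A reader might infer a conflict between protocol and SAP, or a known bias of some magnitude; there is no such conflict, and the range in the working rests on assumed p and r. The conclusion also rests on the readable text: parts of the SAP are redacted, and table specifications are in a separate document that could contain further displays.

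**What to change.** - Keep the End of Study shift, as the protocol requires.
- In SAP 6.2.2, define End of Treatment as the last non-missing post-randomization assessment on or before the end of the treatment period, whatever visit window it falls in.
- In Table 5-21, add a shift from baseline to End of Treatment, labelled 'treatment period'. It should not be labelled 'on drug', because dosing is per attack.
- Show the shift to Visit 16 separately, as Safety Follow-up.
- Optionally, as supportive output only, add a shift to the highest and lowest treatment-period values, which would pick up changes that resolve mid-study. If shown, give the number of laboratory assessments and the follow-up time by arm beside it, because this display rises with the number of assessments. Showing those counts discloses the problem but does not remove it.

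The cost is one definition and one or two extra displays, from data already collected. The optional highest and lowest shifts would add two more, and would look less favourable in every arm.
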